#### 7.4.2 Qualitative analysis

After the completion of individual interviews, recordings will be transcribed. Transcripts will be analyzed in NVivo software, using directed content analysis techniques (Merriam and Tisdell 2016) to identify and organize relevant themes. Codes and coding rules for a codebook will be established by the PI and study staff based on the interview guide and transcripts. When the codebook is established, at least two study staff will independently code transcripts to identify themes and sub-themes, resolving disagreements in coding through discussion. Themes will be summarized and compared across demographic groups (e.g. sex, age, race/ethnicity), activity level (high/low), and sleep duration (longer/shorter). Acceptability of the use of CGM for T2D risk evaluation at home will be rated on a Likert scale (1: completely unacceptable, 2: mostly unacceptable, 3: neutral, 4: mostly acceptable, 5: completely acceptable). Acceptability will be defined as a mean score for all participants of  $\geq$ 3.

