#### 4.1.4 Individual Interview and Disordered Eating Questionnaire

Upon completion of CGM wear, youth participants, with or without their parents at the discretion of the research team, will be invited to participate in a 20-minute semi-structured interview via phone or videoconferencing platform to assess the acceptability of CGM use as an alternative to clinical OGTT for diabetes risk assessment. Interviews will also be used

to elicit barriers and facilitators to diabetes evaluation and follow up for diabetes risk. Interviews will be conducted by study staff and will be audio-recorded and professionally transcribed.

After completion of the interview, participants will be asked to complete a brief, 12-item questionnaire related to disordered eating behaviors in the past 28 days. This will be completed via REDCap. Participants will be allowed to skip questions if they are uncomfortable answering.

Participants will be compensated \$15 for completion of the interview.

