#### **5.4 Individual Interview and Disordered Eating Questionnaire: any time between Day 10 of Observation Period and 1 month after Study Visit**

- Participants (ages 15-18) or their parents (for participants ages 8-14) will be invited to participate in a 30-minute semi-structured individual interview via phone or videoconferencing platform to assess the acceptability of CGM use as an alternative to clinical OGTT for diabetes risk assessment.
- Participants will be asked to complete a brief, 12-item questionnaire related to disordered eating behaviors in the past 28 days. This will be completed via REDCap. Participants will be allowed to skip questions if they are uncomfortable answering
- Participants will be compensated \$15 for completion of the interview.

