### 6.1.6 Interview and Disordered Eating Questionnaire

Semi-structured individual interviews will be conducted by study staff after the observation period to evaluate acceptability of use of CGM for diabetes risk assessment, including barriers and facilitators to this approach. Interviews will be audiorecorded and then professionally transcribed for qualitative analysis using NVivo software.

The disordered eating questionnaire includes 12 questions that inquire about the feeling of “loss of control” when eating. This questionnaire does not have a validated threshold for normal versus abnormal and is not in clinical use in its form in this study.

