## **6.2 Efficacy Evaluations**

CGM data completeness (data available for  $\geq 80\%$  requested days worn), nutrition logging quality and completion ( $\geq 80\%$  of participants documenting date and time of glucose challenge, mixed meal challenge, or both), and acceptability (mean score  $\geq 3$ , or “neutral” for all participants) will be used to determine feasibility and acceptability of this approach.

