### **7.5 Sample Size and Power**

The sample size for this pilot study balances feasibility with the likelihood of obtaining meaningful results for future studies. Assuming 20% drop-out or incomplete data, a sample size of 40 should lead to 32 evaluable subjects. This will allow for subgroup analyses, including by sex and physical activity strata (high versus low). This study will include nearly twice as many participants with known dysglycemia (or more if previously undiagnosed) as those without in order to maximize the ability to compare impaired glucose tolerance and abnormal CGM-measured glucose trends.

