**Interview and disordered eating questionnaire:** Potential risks include momentary embarrassment or discomfort as well as breach of privacy and confidentiality. Participants may decline to answer any question during the interview for any reason. Every precaution will be taken to secure participants' personal information to ensure confidentiality.

**Sharing of private health information (PHI):** There is the potential risk for a breach of confidentiality. Private health information will be collected, accessed and stored according to HIPAA guidelines, including the use of multilevel password protection and enforcement of system user privileges on the database. To limit the risk of disclosure to the minimum necessary to conduct the study, all direct identifiers will be removed as soon as possible and codes will be substituted for personal identifiers. Records of individuals are stored with ID

---

numbers and a code with no discernible personal identifiers. Code lists and data files will be stored in separate, secure locations. Data will be stored on institutional secure servers hosted and accessed on password-protected computers. To maintain confidentiality, codes will be used in the database, presentations and publications.

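### The acceptability rule does not say when or from whom the 1–5 rating is collected; the only route described is a voluntary interview, so the mean probably omits some participants and is fragile near the bar of 3

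*Combined protocol and SAP*

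**What the plan says.** Section 7.4.2 of the protocol introduces the scale: "Acceptability of the use of CGM for T2D risk evaluation at home will be rated on a Likert scale", from 1 (worst) to 5 (best), with 3 as the neutral midpoint. The pass rule follows: "Acceptability will be defined as a mean score for all participants of" 3 or more. The synopsis and section 6.2 repeat the bar. None of these places gives the time, the instrument or the respondent for the rating.

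Every procedure tied to acceptability is the interview after wear. Section 6.1.6 says: "Semi-structured individual interviews will be conducted by study staff after the observation period to evaluate acceptability of use of CGM for diabetes risk assessment". Section 4.1.4 says that youth, with or without parents as the research team decides, "will be invited to participate in a 20-minute semi-structured interview via phone or videoconferencing platform". Section 5.4 assigns the respondent by age: "Participants (ages 15-18) or their parents (for participants ages 8-14) will be invited to participate in a 30-minute semi-structured individual interview". Section 9.3.2 adds: "Participants may decline to answer any question during the interview for any reason". Table 1 lists no other acceptability instrument.

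Section 5.6.1 asks those who withdraw to do the interview, in order to learn why they stopped. Section 7.4.4, on missing data, deals only with gaps in the CGM trace. By contrast, H1b in section 7.4.1 names its denominator as the whole study group.

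**The concern.** Acceptability is in the study title, is one of two secondary endpoints, and has a pass/fail rule. The rule speaks of everyone in the study, yet the only visible source of ratings is a step that people may refuse in whole or in part. It can also fall up to about a month after the visit. Little money depends on it: under section 9.6.2 the $100 is paid when the devices come back, and only $15 is for the interview.

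If people who disliked the device or the home challenge skip the call more often than others, the mean over raters will be higher than the mean over the cohort. The bar is only neutral, so a pass close to 3 is the result most exposed to this. No rule says what to do with a missing rating, so a reader of the final report could not tell whether the stated mean describes the cohort or a self-selected part of it.

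**Working it through.** **The plan's own figure.** Section 7.5 enrols 40 and allows for loss: "Assuming 20% drop-out or incomplete data". 40 × (1 − 0.20) = 32 evaluable, as stated. The plan gives no precision or power figure for acceptability, so there is none to reproduce.

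**Inputs**
- N = 40 enrolled (section 4.2.2, section 7.5).
- Bar = 3 on a 1–5 scale (section 7.4.2).
- m = number unrated. The plan gives no value, so 4, 8 and 12 are assumed. The middle value equals the count lost under section 7.5, but that allowance is not an interview non-response rate.
- s = score that non-raters would have given. Assumed to be 1 (the worst case) or 2.
- r = 40 − m raters.

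**Formulas**
- Full-cohort mean = (r × observed mean + m × s) / 40.
- Setting this to 3 gives the break-even observed mean = (120 − m × s) / r.

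| Unrated m | Raters r | Break-even, s = 1 | Break-even, s = 2 |
|---|---|---|---|
| 4 | 36 | (120 − 4)/36 = 3.22 | (120 − 8)/36 = 3.11 |
| 8 | 32 | (120 − 8)/32 = 3.50 | (120 − 16)/32 = 3.25 |
| 12 | 28 | (120 − 12)/28 = 3.86 | (120 − 24)/28 = 3.43 |

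An observed mean between 3 and the break-even value passes the rule as computed on raters and fails it on the full cohort.

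**Illustrations**
- Observed 3.4, m = 8: (32 × 3.4 + 8 × 1)/40 = 2.92, a fail; (32 × 3.4 + 8 × 2)/40 = 3.12, a pass.
- Observed 4.0, m = 12, s = 1 (the harshest case shown): (28 × 4.0 + 12 × 1)/40 = 3.10, a pass.

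**The case against.** Several points on the other side are fair.

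- **Source of the rating.** No sentence says that the item is asked in the interview. A reader might infer that the plan definitely restricts the score to interviewees. The documents do not show that: it is an inference from the item's place among the interview analyses and from the absence of any other instrument. The interview guide that section 7.4.2 mentions is not in the documents. If another collection point is intended, the plan still needs to state it.
- **Meaning of the rule.** Its reference to all participants comes shortly after a sentence on comparing themes between demographic, activity and sleep groups. It may mean one pooled mean rather than a promise of 40 scores. That softens the mismatch, but missing ratings remain without a rule under either reading.
- **Rate of loss.** A reader might take the 20% in section 7.5 as the expected share without a rating. It is an allowance for drop-out or incomplete data in general. A participant with poor CGM or log data can still give a rating.
- **Direction of bias.** A reader might conclude that the score is biased upward. Nothing in the documents links missing the interview to dislike of the approach; scheduling or failed contact could explain it too. Upward bias is plausible, not shown.
- **Mitigation.** The interview is remote, paid and has a wide window, and withdrawn participants are asked to take part. This reduces the gap. It does not close it: the request is voluntary, is aimed at reasons for stopping, and does not reach completers who decline the call or the item.
- **The remedy.** A text item can also go unanswered, and it could change the rater. Section 4.1.2 sends texts to the participant, or to a parent if the participant has no texting phone, whereas section 5.4 sets the respondent by age. This objection stands and shapes the fix.

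**Conclusion.** The point holds as a modest, low-cost improvement. The plan leaves open when and from whom the rating is collected. On the procedures it does describe, the mean will probably cover only people who accept a voluntary interview and answer the item.

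The effect depends on how close the result lies to the bar. With 8 of 40 unrated, the verdict could reverse for an observed mean from 3.0 up to 3.50 if non-raters would score 1, or up to 3.25 if they would score 2. With 4 unrated the upper limits fall to 3.22 and 3.11; with 12 they rise to 3.86 and 3.43. A mean of 4.0 is safe throughout. The counts unrated and the scores given to non-raters are assumptions, not figures from the plan.

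**What to change.** 1. Collect the single 1–5 item from every enrolled participant at Day 10, or at early device removal, through the existing text/REDCap survey. Texts already go out three times a day (section 5.3.1), and the CGM comes off at midday on Day 10 (section 5.3.4), so a later text that day can carry the item. Keep the interview for qualitative content and as a back-up for those who have not answered.
2. State in advance whose rating counts, youth or parent. Reconcile sections 4.1.2, 4.1.4 and 5.4, which point to different respondents.
3. Report the number rated out of 40 and the mean with a 95% CI.
4. Prespecify two sensitivity means over all 40, with non-raters scored 1 and scored 2.

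The cost is one extra survey item and two lines of reporting. Some text non-response will remain, which is why items 3 and 4 are still needed. The reported figure may be slightly less favourable.

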#### 7.4.3 Exploratory analyses

The analyses for at-home glucose challenge described above will be repeated to evaluate the test performance of at-home mixed-meal challenge in comparison to 2-hour OGTT. In addition, CGM metrics such as average, area under the curve, and peak glucose as well as coefficient of variation will be compared for days of CGM wear without glucose or mixed-meal challenge versus challenge days to assess the difference in glucose trends of typical daily life versus those artificially imposed by testing.

An additional exploratory analysis will use responses from the disordered eating questionnaire to assess whether correlations between OGTT and CGM-measured glycemia differ between youth with higher versus lower self-report of loss-of-control eating.

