An additional important research question relates to the impact of disordered eating, most notably loss-of-control (LOC) eating, on glycemia. Disordered eating, including the consumption of objectively large amounts of food in one sitting, is common among youth with obesity and type 2 diabetes (TODAY Study Group 2011). The amount of carbohydrate and other nutrients consumed in a real-life, non-lab setting may be significantly larger than that provided in a standard oral glucose tolerance test, potentially leading to greater discrepancy between at-home and lab-based measures of glycemia in youth with disordered (LOC) eating than those without this tendency.

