#### 4.1.2 Study Visit

After study procedures are reviewed and questions answered, written informed consent and assent (participants<18) will be obtained if not already obtained electronically via REDCap. Participants will arrive after overnight fast (minimum 10 hours) and will undergo physical examination by a pediatric endocrinologist as well as anthropometrics, vital sign measurement, questionnaires (medical, family, social history), and 2-hour OGTT performed according to American Diabetes Association criteria.(American Diabetes Association Professional Practice, American Diabetes Association Professional Practice et al. 2022) After baseline (time 0) venous blood sample, participants will ingest glucose solution (1.75 g/kg body weight, max 75g) within 5 minutes or less. Additional venous blood samples will be obtained at timed intervals after ingestion to determine plasma glucose, insulin, and c-peptide

(30, 60, 90, 120 min) . HbA1c will also be measured (one venous blood sample). During OGTT, Dexcom G6 Pro (blinded, no data visible to participant) CGM will be placed on the participant's abdomen by study staff trained in CGM placement. Participants will be assigned a unique study ID for use with Dexcom and survey collection. Participants (or their parent if the participant does not have a phone with text messaging capability) will also be registered for text message-based surveys via Mosio, a text messaging platform for clinical research, and will be instructed on nutrition, activity, and sleep logging to be completed during the 10-day CGM wear period. Paper logbooks will be provided for use in case of technical difficulties with texts. Participants will be provided with a wrist-worn actigraphy device (ActiGraph GT9X Link) to wear continuously during the 10-day period for collection of objectively measured activity and sleep data to define periods of eating, overnight fasting, and exercise.

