#### 4.1.3 Observation Period

Participants will be instructed to participate in their typical daily routines, with the exception of two at-home challenges: 1) glucose, and 2) mixed-meal. The ***at-home glucose challenge*** will serve as the primary comparison to the laboratory-measured OGTT. For this challenge, participants will be asked to drink the same glucose solution (Trutol) consumed as part of the OGTT at PCTRCC and provided with the appropriate weight-based amount. They will be instructed to choose a day between days 3 and 9 of the study period during which they will be able to fast for at least 10 hours, drink the glucose beverage, and then be inactive for 2 hours. They will log the date and time of glucose ingestion. For the ***at-home mixed-meal challenge***, participants will be asked to choose a day between study days 3 and 9, separate from the glucose challenge day, during which they will be able to fast for at least 10 hours, eat a snack or meal with at least 50 grams of carbohydrate as well as fat and protein content, and then be inactive for 2 hours. All participants and families will be instructed on determination of carbohydrate content using example foods that they typically consume. Participants will receive \$20 for travel to the study visit, loaded onto a university payment card.

***Text message-based surveys and actigraphy:*** Participants will be sent surveys 3 times daily via text message, inquiring about food and drink intake, physical activity, and time in bed (start/stop times). Survey responses will be collected via Mosio and entered in Research Electronic Data Capture (REDCap), a secure, web-based application for clinical research data collection. Branching logic will be used in REDCap so that participants will only need to provide detail for relevant activities each time. As an incentive for ActiGraph wear, participants will earn an additional \$20 if the ActiGraph device is worn for at least 8/10 days.

***Study completion:*** On day 10 of CGM wear (or earlier in case of discomfort), participants will remove the sensor and transmitter at home by simply peeling off the device. Transmitter and ActiGraph will be returned to the study team by participants using prepaid shipping envelopes or in-person if preferred. Upon receipt of the transmitter and ActiGraph, participants will receive compensation for participation in the study (\$100).

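### Section 7.4.3 compares OGTT–CGM correlations by loss-of-control eating, but Section 2.3 asks about a larger discrepancy, which a correlation can miss; the paired difference should be reported alongside (low importance)

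*Combined protocol and SAP*

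**What the plan says.** Section 2.3 gives the reason for collecting the disordered-eating questionnaire. It argues that food "consumed in a real-life, non-lab setting may be significantly larger than that provided in a standard oral glucose tolerance test". From this it draws its hypothesis, which it words as "potentially leading to greater discrepancy between at-home and lab-based measures of glycemia in youth with disordered (LOC) eating". That is a statement about a difference between two measurements, with a suggested direction.

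Section 7.4.3 gives the analysis: to "assess whether correlations between OGTT and CGM-measured glycemia differ between youth with higher versus lower self-report of loss-of-control eating". Section 7.4.1 states that correlation analyses will be Spearman or Pearson, depending on distribution.

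Nothing else in the plan fills the gap:
- The correlation subgroups listed in Section 7.4.1 do not name loss-of-control eating, and they concern correlations too.
- Section 7.4.3 also compares CGM metrics between challenge and non-challenge days, but neither by questionnaire score nor against OGTT.
- The covariates named in Section 7.3 do not include the score.
- No paired-difference or agreement analysis is planned, overall or by score.

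Section 7.4.3 does not say which CGM measure is meant. For the at-home glucose challenge, Section 4.1.3 says that "participants will be asked to drink the same glucose solution (Trutol) consumed as part of the OGTT", in a weight-based amount.

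**The concern.** A correlation describes how well two measurements order participants and how tightly they follow a line. It does not describe how far apart they are. If youth with loss-of-control eating run higher on CGM than their OGTT suggests, and by a similar amount each, their correlation looks the same as everyone else's. The study could then report no difference by loss-of-control eating even though the discrepancy described in Section 2.3 is present.

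The choice of CGM measure matters as well. The proposed mechanism is larger intake in daily life. The glucose challenge repeats the OGTT drink in a set amount, so a measure taken only from that challenge does not capture the mechanism.

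What is at stake is one exploratory conclusion, and the signal it passes to later studies.

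**Working it through.** **Inputs from the documents.** Section 7.5 states that "a sample size of 40 should lead to 32 evaluable subjects". Check: 40 × (1 − 0.20) = 32. The r = 0.5 is the value Section 2.3 cites from an earlier study of free-living CGM in youth. The two-sided 0.05 level is in the synopsis.

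**Assumed inputs.** r = 0.7 as an alternative; SD 30 mg/dL for each measure; groups of 16/16 or 22/10; shifts of 10 to 40 mg/dL. Section 7.4.3 names no test, so the rejection rates below are only a yardstick of visibility.

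**1. Invariance.** For OGTT value x, CGM value y, any constant a and any b > 0:

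corr(x, a + by) = b·cov(x, y) / [SD(x) · b·SD(y)] = corr(x, y).

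Ranks are also unchanged, so Spearman's coefficient does not move either. In one simulated group of 16, adding 10, 20 or 40 mg/dL to CGM left Pearson at −0.038 and Spearman at 0.141, while the mean difference went from −6.8 to 3.2, 13.2 and 33.2 mg/dL. Multiplying CGM by 1.3 left both coefficients unchanged and moved the mean difference to 34.3 mg/dL.

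**2. Uniform shift in the higher group** (20,000 simulated trials per row; Fisher z contrast of the two correlations against a t-test on CGM minus OGTT; shifts of 10/20/30/40 mg/dL):

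| r | Split | Correlation contrast | Mean difference |
|---|---|---|---|
| 0.5 | 16/16 | 4.7/4.8/5.0/4.8% | 15/44/78/96% |
| 0.5 | 22/10 | 5.0/5.0/4.8/4.9% | 14/39/72/92% |
| 0.7 | 16/16 | 4.8/4.8/5.0/4.9% | 22/65/94/>99% |

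The correlation contrast stays at the false-positive rate whatever the shift.

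**3. More variable discrepancy, no shift.** Write CGM and OGTT as shared glycemia plus error, with total variance 1. At r = 0.5, doubling the CGM error SD in high scorers gives r = 0.5/√(0.5 + 4 × 0.5) = 0.32; tripling gives 0.5/√(0.5 + 9 × 0.5) = 0.22. At r = 0.7 the values are 0.7/√(0.7 + 4 × 0.3) = 0.51 and 0.7/√(0.7 + 9 × 0.3) = 0.38. In simulation with 16/16, the correlation contrast flags these in 9% and 14% of runs (r = 0.5), and 12% and 23% (r = 0.7). The expected mean difference is unchanged by pure scatter, so it cannot show this pattern.

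**4. What a correlation contrast can resolve.** SE of the Fisher z difference = √(1/13 + 1/13) = 0.392. For 80% power the gap must be (1.96 + 0.84) × 0.392 = 1.10. From r = 0.50 (z = 0.549), that means the other group at −0.50 or 0.93. For 0.5 against 0, power is about 29%.

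**5. Precision of the added comparison.** SD of the difference = 30 × √(2(1 − r)), which is 30 mg/dL at r = 0.5 and 23.2 at r = 0.7. With 16/16, the 95% CI half-width is 2.042 × SD × √(1/16 + 1/16): about 21.7 mg/dL at r = 0.5 and 16.8 at r = 0.7.

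**The case against.** **It is exploratory.** Loss-of-control eating appears in no primary or secondary objective or endpoint, and the study is a 40-person pilot. This stands, and it sets the importance at low. It does not remove the mismatch between the question and the statistic.

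**Discrepancy need not mean a uniform shift.** Section 2.3 does not say every affected youth is displaced equally. If intake varies, the discrepancy also appears as scatter, which lowers r and leaves the mean difference alone. This stands too. A reader might infer that the correlations should be replaced; step 3 shows why they should not.

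**Subtraction can mislead when scales differ.** It is tempting to subtract the mean of the OGTT samples from a whole-day CGM mean. The two need not share a scale. If CGM responds at a fraction of the OGTT scale and higher scorers have higher glycemia, the difference falls as the score rises. In simulations with assumed scale factors of 0.8 to 0.5 and score–glycemia correlations of 0.3 to 0.5, a regression of the difference on the score was falsely significant in 6% to 33% of runs. Most of these errors were negative, which would hide the effect sought. Subtraction should be confined to like-for-like 2-hour values.

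**The grouping.** Section 6.1.6 says "This questionnaire does not have a validated threshold for normal versus abnormal". A reader might infer that the higher/lower split is invalid. The documents do not support that: a relative split needs no normal/abnormal cut-off. The absent scoring rule, and the lack of handling for skipped items (Section 5.4: "Participants will be allowed to skip questions if they are uncomfortable answering"), are missing detail.

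**Fewer than 32 may contribute.** The questionnaire follows an interview that participants are invited to join. At an assumed 12/12, the half-width in step 5 becomes 2.074 × 30 × √(1/12 + 1/12) = 25.4 mg/dL at r = 0.5.

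**Conclusion.** The point holds as a cheap improvement of low importance. The planned contrast cannot see a systematic CGM-above-OGTT discrepancy in high scorers, and no other part of the plan looks for one. That blindness is algebra and rests on no assumption. Its size does rest on assumptions: with SD 30 mg/dL, r = 0.5 and 16/16, a 20 to 30 mg/dL shift is visible in about 5% of trials by correlations and in 44% to 78% by mean differences.

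The documents do not support going further. They do not show that such a shift exists, so the plan could miss a discrepancy rather than certainly will. The planned correlations keep a use. Neither statistic is precise at about 32 participants. The feasibility endpoints, the AUC for CGM-2h and the acceptability rating do not depend on this analysis.

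**What to change.** Edit Section 7.4.3 only.

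1. Keep the planned correlations, since they respond to scatter that a mean difference does not show.
2. Add each participant's 2-hour CGM value after the glucose challenge minus OGTT-2h, and the same after the mixed meal. Section 7.4.3 already sets the mixed meal against the 2-hour OGTT. Report the mean and SD of each difference in the higher and lower groups, and the between-group difference in means with a 95% CI.
3. Plot the difference against the questionnaire score, so that a graded shift or widening scatter can be seen without relying on the split.
4. Compare by score one non-challenge-day CGM measure that Section 7.4.3 already derives (average or peak). Do this descriptively and without subtracting OGTT values. It is the part closest to the free-living mechanism in Section 2.3.

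The cost is a few sentences and a little more analysis, with no new data or participant burden. The results will be imprecise at about 32 participants or fewer and should be reported as exploratory.
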